11.0 REPORTING OF ADVERSE EVENTS

11.1 Adverse Event and Reporting Definitions

An adverse event (AE) is any new untoward medical occurrence or worsening of a preexisting medical condition in a patient or clinical investigation subject who has been administered a study drug and which does not necessarily have to have a causal relationship with this treatment. An AE can therefore be any unfavorable and unintended sign (including an abnormal laboratory finding, for example), symptom, or disease temporally associated with the use of a medicinal product, whether or not considered related to the medicinal product. Data on adverse events will be collected and reported regardless of relation to the study drug. Moreover, relatedness of these AE to the use of BMS drugs associated with this study (where applicable) will be assessed.

Note: Although not always considered adverse events by regulatory definition, the following events associated with a BMS product must be reported.

- Exposure (to fetus) during pregnancy, exposure (to infant) during lactation, and paternal exposure
- Overdose
- Lack of efficacy
- Abuse
- Misuse
- Off-label use
- Occupational exposure
- Medication error and potential medication error
- Suspected transmission of an infectious agent, e.g., any organism, virus or infectious particle pathogenic or non-pathogenic, via the medicinal product.

The causal relationship to the study drug associated with this study is determined by the PI and should be used to assess all adverse events (AE). The causal relationship can be one of the following:

- Related: There is a reasonable causal relationship between the BMS product associated with this study and the AE.
- Not related: There is not a reasonable causal relationship between the BMS product associated with this study and the AE.
- The term "reasonable causal relationship" means there is evidence to suggest a causal relationship.

Adverse events can be spontaneously reported or elicited during open-ended questioning, examination, or evaluation of a subject. (In order to prevent reporting bias, subjects should not be questioned regarding the specific occurrence of one or more AEs.)

NON-SERIOUS ADVERSE EVENT

- Non-serious Adverse Events (AE) are to be provided to BMS in aggregate via interim or final study reports as specified in the agreement or, if a regulatory requirement [e.g. IND US trial] as part of an annual reporting requirement.
- Non-serious AE information should also be collected from the start of a placebo lead-in period or other observational period intended to establish a baseline status for the subjects.

A *non-serious adverse event* is an AE not classified as serious.

A *serious AE (SAE)* is any untoward medical occurrence that at any dose: results in death; is life-threatening (defined as an event in which the subject was at risk of death at the time of the event; it does not refer to an event which hypothetically might have caused death if it were more severe); requires inpatient hospitalization or causes prolongation of existing hospitalization (PI determines if the hospitalization event is considered SAEs); results in persistent or significant disability/incapacity; is a congenital anomaly/birth defect; is an important medical event (defined as a medical event(s) that may not be immediately life-threatening or result in death or hospitalization but, based upon appropriate medical and scientific judgment, may jeopardize the subject or may require intervention [e.g., medical, surgical] to prevent one of the other serious outcomes listed in the definition above.) Examples of such events include, but are not limited to, intensive treatment in an emergency room or at home for allergic bronchospasm; blood dyscrasias or convulsions that do not result in hospitalization.); suspected transmission of an infectious agent, pathogenic or nonpathogenic, via the BMS product associated with this study is an SAE.

An *overdose* is defined as the accidental or intentional administration of any dose of a product that is considered both excessive and medically important.

Although pregnancy, overdose; potential drug-induced liver injury (DILI) and cancer are not always serious by regulatory definition, these events are handled as SAEs.

The following hospitalizations are not considered SAEs in BMS clinical studies:

- A visit to the emergency room or other hospital department < 24 hours that does not result in admission (unless considered an important medical or life-threatening event).
- Elective surgery, planned prior to signing consent.
- Admissions as per protocol for a planned medical/surgical procedure
- Routine health assessment requiring admission for baseline/trending of health status (e.g., routine colonoscopy).
- Medical/surgical admission other than to remedy ill health and planned prior to entry into the study. Appropriate documentation is required in these cases
- Admission encountered for another life circumstance that carries no bearing on health status and requires no medical/surgical intervention (e.g., lack of housing, economic inadequacy, caregiver respite, family circumstances, administrative reasons).
- Admission for administration of subsequent anti-cancer therapy in the absence of any other SAEs (applies to oncology protocols).

Laboratory Test Abnormalities

All laboratory test results captured as part of the study should be recorded following institutional procedures. Test results that constitute SAEs should be documented and reported as such. The following laboratory abnormalities should be documented and reported appropriately:

- Any laboratory test result that is clinically significant or meets the definition of an SAE
- Any laboratory abnormality that required the participant to have study drug discontinued or interrupted
- Any laboratory abnormality that required the subject to receive specific corrective therapy.

It is expected that wherever possible, the clinical rather than laboratory term would be used by the reporting investigator (e.g., anemia versus low hemoglobin value).

Potential Drug Induced Liver Injury (DILI)

Wherever possible, timely confirmation of initial liver-related laboratory abnormalities should occur prior to the reporting of a potential DILI event. All occurrences of potential DILIs, meeting the defined criteria, must be reported as SAEs.

Potential drug induced liver injury is defined as:

- 1) AT (ALT or AST) elevation > 3 times upper limit of normal (ULN) AND
- 2) Total bilirubin > 2 times ULN, without initial findings of cholestasis (elevated serum alkaline phosphatase), AND
- 3) No other immediately apparent possible causes of AT elevation and hyperbilirubinemia, including, but not limited to, active myositis with elevated CK, viral hepatitis, pre-existing chronic or acute liver disease, or the administration of other drug(s) known to be hepatotoxic.

Pregnancy

If, following initiation of the investigational product, it is subsequently discovered that a study participant is pregnant or may have been pregnant at the time of investigational product exposure, including at least 5 half-lives after product administration, the investigational product will be permanently discontinued in an appropriate manner (e.g., dose tapering if necessary for participant).

The investigator must immediately notify [contact] of this event via the Pregnancy Surveillance Form in accordance with SAE reporting procedures.

Protocol-required procedures for study discontinuation and follow-up must be performed on the participant.

Follow-up information regarding the course of the pregnancy, including perinatal and neonatal outcome and, where applicable, offspring information must be reported on the Pregnancy Surveillance Form [provided upon request from BMS]

Any pregnancy that occurs in a female partner of a male study participant should be reported to BMS. Information on this pregnancy will be collected on the Pregnancy Surveillance Form. In order for Sponsor or designee to collect any pregnancy surveillance information from the female partner, the female partner must sign an informed consent form for disclosure of this information.

Overdose

An overdose is defined as the accidental or intentional administration of any dose of a product that is considered both excessive and medically important. All occurrences of overdose must be reported as an SAE.

Other Safety Considerations

Any significant worsening noted during interim or final physical examinations, electrocardiograms, X-rays, and any other potential safety assessments, whether or not these procedures are required by the protocol, should also be recorded as a non-serious or serious AE, as appropriate, and reported accordingly.

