3.3.1 Primary Outcome Measures

The primary outcome criteria for efficacy will be the FVC% change from the baseline visit to week 24 between the 2 treatment arms (SOC/placebo vs. SOC/ABT). An intention to treat analysis will be used. Ranked ANCOVA will be used with average standardized rank change in the predicted FVC% as the outcome measure and the standardized rank baseline as a covariate. Primary outcome criteria for safety and tolerability will be adverse events (routine adverse events or tolerability issues and serious adverse event) between the 2 treatment arms (SOC/placebo vs. SOC/ABT). Chi-square (or Fischer exact test) and t-test (or Mann-Whitney) will be used based on data variable and distribution.

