4.5.2 ILD Worsening Criteria

If any one of the criteria is met after 8 weeks of therapy:

- a. FVC% decline $\geq 30\%$ from baseline PFT
- b. HRCT chest suggesting severe worsening in the ILD as compared to baseline (clinician/radiologist interpretation)
- c. Hospitalization with severe ILD with new or increased long term O2 requirement related to worsening ILD
- d. Severe worsening in clinical dyspnea due to ILD as determined by patient and treating physician. Note that meeting “worsening criteria” doesn’t automatically mean administration of rescue therapy. Rescue therapy is given if patient meeting worsening criteria AND treating physician believe clinical disease warrants a change in therapy.

Subjects meeting these criteria will be considered treatment failures but can continue to receive study drug if deemed reasonable by the managing clinician or investigator. If at any time a worsening in condition occurs, the subject should be seen for an unscheduled study visit. A subject irrespective of worsening or rescue medication use, can enter the open label phase (II) of the study at the end of the 24 week period of phase I.

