11.2 Reporting of Serious Adverse Events Associated with Abatacept

Immediate Reporting Requirements:

Non-serious AEs and SAEs whether or not related to the BMS product associated to this study, pregnancies, AEs associated with maternal exposure, and pregnancy outcomes ascertained in the study must be reported individually in the time frames noted below. All AEs collected will also be reported in aggregate in the final study report. Any component of a study endpoint that is considered related to study therapy (e.g., death is an endpoint, if death occurred due to anaphylaxis, anaphylaxis must be reported) should be reported as an SAE.

Serious Adverse Event Collection and Reporting

- All Serious Adverse Events (SAEs) that occur following the subject's written consent to participate in the study through 30 days of discontinuation of dosing must be reported to BMS Worldwide Safety. If applicable, SAEs must be collected that relate to any later protocol-specified procedure (e.g., a follow-up skin biopsy).
- The MedWatch form 3500A will be used to report SAEs. The form will be reviewed and approved by BMS. The BMS protocol ID number must be included on whatever form is submitted by the Sponsor/Investigator. The form can be accessed at: <http://www.accessdata.fda.gov/scripts/medwatch/>.
- Following the subject's written consent to participate in the study, all SAEs, whether related or not related to study drug, are collected, including those thought to be associated with protocol-specified procedures. The investigator should report any SAE occurring after these time periods that is believed to be related to study drug or protocol-specified procedure. For drugs with potential for delayed SAEs (e.g., delayed excretion of the parent or active metabolites), a longer follow-up period may be warranted to allow collection of these SAEs Laboratory tests, and other assessments.
- For studies with long-term follow-up periods in which safety data are being reported, include the timing of SAE collection.

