SAEs, whether related or not related to study drug, as well as pregnancies, must be reported to BMS within 24 hours. SAEs must be recorded on the MedWatch form; pregnancies must be reported on a Pregnancy Surveillance Form.

- An SAE report should be completed for any event where doubt exists regarding its seriousness.
- For studies with long-term follow-up periods in which safety data are being reported, include the timing of SAE collection in the protocol.
- If the investigator believes that an SAE is not related to study drug, but is potentially related to the conditions of the study (such as withdrawal of previous therapy or a complication of a study procedure), the relationship should be specified in the narrative section of the SAE Report Form.
- If only limited information is initially available, follow-up reports are required. (Note: Follow-up SAE reports should include the same investigator term(s) initially reported.)

If an ongoing SAE changes in its intensity or relationship to study drug or if new information becomes available, a follow-up SAE report should be sent within 24 hours to BMS (or designee) using the same procedure used for transmitting the initial SAE report. All SAEs should be followed to resolution or stabilization.

Non-serious Adverse Event Collection and Reporting

The collection of non-serious AE information should begin at initiation of study drug. All non-serious adverse events (not only those deemed to be treatment-related) should be collected continuously during the treatment period and for a minimum of 30 days following the last dose of study treatment.

All non-serious AEs must be reported by confirmed fax transmission or reported via electronic mail to:

Non-serious AE Email Address: [contact]

Non-serious AE [contact]

Non-serious AEs should be followed to resolution or stabilization, or reported as SAEs if they become serious. Follow-up is also required for non-serious AEs that cause interruption or discontinuation of the BMS product associated with this study and for those present at the end of the study, as appropriate.

MedWatch 3500A Reporting Guidelines

In addition to completing appropriate patient demographic and suspect medication information, the report should include the following information within the Event Description (section 5) of the MedWatch 3500A form:

- Treatment regimen (dosing frequency, combination therapy)
- Protocol description (and number, if assigned)

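### The hospitalization criterion for an SAE is left to the PI without criteria, so an unplanned admission can drop out of the SAE comparison and the 24-hour report

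*Combined protocol and SAP*

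**What the plan says.** Section 11.1 lists the criteria that make an adverse event serious. The hospitalization criterion reads "requires inpatient hospitalization or causes prolongation of existing hospitalization (PI determines if the hospitalization event is considered SAEs". Nothing says on what basis the PI decides. Death, life-threatening events, lasting disability and congenital anomaly carry no such parenthesis.

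The same section then gives a list that opens "The following hospitalizations are not considered SAEs in BMS clinical studies". It has seven entries: short emergency visits without admission, elective surgery planned before consent, protocol-planned procedures, routine health assessments, pre-planned admissions not meant to treat illness, social or administrative admissions, and admissions for later anti-cancer therapy.

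Section 11.2 adds three relevant rules. On doubtful cases: "An SAE report should be completed for any event where doubt exists regarding its seriousness". On scope, after consent "all SAEs, whether related or not related to study drug, are collected". On timing, SAEs go to the manufacturer within 24 hours. Section 11.1 defines an AE to include "any new untoward medical occurrence or worsening of a preexisting medical condition".

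On the efficacy side, section 4.5.2(c) makes this an ILD worsening event after 8 weeks of therapy: "Hospitalization with severe ILD with new or increased long term O2 requirement related to worsening ILD". A subject who meets it is a treatment failure.

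Section 3.3.1 states: "Primary outcome criteria for safety and tolerability will be adverse events (routine adverse events or tolerability issues and serious adverse event". Sections 12.2.1 and 12.3 repeat this, and section 3.3.3 plans to compare the proportion of SAEs between arms.

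**The concern.** Hospitalization is normally a factual trigger for seriousness: the patient was admitted or was not. The parenthesis turns it into a matter of discretion, and no stated limit or central review of seriousness stands behind it. A PI could class an unplanned pneumonia or ILD admission as non-serious under the parenthesis, while another PI who relied on the exemption list would report the same admission as an SAE.

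These admissions matter in a trial that adds an immunomodulator to steroids, mycophenolate or azathioprine in patients with ILD. They are also the ones that could be taken for the expected course of the disease, since an ILD hospitalization is already an efficacy event. What is at stake is the SAE count by arm, which belongs to the primary safety outcome, and the expedited report. Section 12.1 names safety and tolerability data as one purpose of this 20-patient pilot.

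**Working it through.** The point rests on no sample size, power or event figure in the plan, so there is none to reproduce. The check is a comparison of text, followed by simple arithmetic on size.

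**Step 1. An unplanned admission for worsening ILD, read without the parenthesis.**
- It is an AE, because worsening of an existing condition qualifies (11.1).
- It meets the hospitalization criterion (11.1).
- It matches none of the seven exempt entries (11.1).
- It is collected whether or not it is related to study drug (11.2).
- Result: it is an SAE, reportable within 24 hours.

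**Step 2. The same admission, read with the parenthesis.** The PI may decide that it does not count. No provision exempts it, but the hospitalization criterion no longer compels the report. The life-threatening and important-medical-event criteria remain and would catch some admissions, not necessarily all.

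**Step 3. What else could push towards omission.** Section 11.2 asks for SAE reporting of "Any component of a study endpoint that is considered related to study therapy". A site could read this as excusing endpoint events judged unrelated, although the all-SAE rule in the same section says otherwise.

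**Step 4. What a reclassified admission loses and keeps.**
- Lost: its place in the SAE comparison (3.3.3), the 24-hour report, and the three-monthly reconciliation of SAE cases (11.2).
- Kept after dosing starts: its record as a non-serious AE, which is still part of the primary safety outcome, and its count as treatment failure if it meets 4.5.2(c) after 8 weeks.
- Before dosing: section 11.2 starts SAE collection at consent and non-serious collection at first study drug. An admission reclassified in the up to 21 days between screening and Visit 1 (7.2) might not be collected, unless the general line in 11.1 on baseline observation periods is taken to cover screening. This does not affect the comparison between arms.

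**Step 5. Size.** Inputs are 20 subjects at 5 sites (3.1.1) and 10 per arm (12.1).
- Shift per patient whose only SAE is reclassified: 1/10 = 10 percentage points in that arm.
- Average site size: 20/5 = 4 patients.
- Two-sided Fisher exact p-values for assumed numbers of patients with an SAE, 10 per arm (illustration only):

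| SAE patients | p | After one reclassification | p |
|---|---|---|---|
| 5 vs 0 | 0.033 | 4 vs 0 | 0.087 |
| 7 vs 1 | 0.020 | 6 vs 1 | 0.057 |
| 3 vs 1 | 0.58 | 2 vs 1 | 1.00 |

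In these examples one reclassified patient crosses 0.05 only when the imbalance is already large. Otherwise the effect is on the reported proportions.

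**The case against.** The strongest defence is that the parenthesis merely names who applies the exemption list. Some entries do need judgement, such as whether an admission was for something other than ill health, or whether a short emergency visit was medically important. On that reading nothing conflicts. The doubt rule can also stand beside a PI decision: a PI who decides, and reports when unsure, satisfies both.

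Much of this stands. A reader might infer that the parenthesis contradicts a closed list, but the plan never calls the list closed or exhaustive. Other lists in section 11.1 are marked as open and this one is not, which is suggestive but no more. Tension is the right word for both the list and the doubt rule.

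A reader might also infer that sites will apply different thresholds. The term PI is not defined. Its use for patient-level decisions in sections 4.2 and 4.5.3 suggests the site investigator, but elsewhere the protocol writes site investigator in full. A single overall PI would remove the variation between sites, though not the lack of criteria.

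Finally, a reader might infer that ILD admissions will be left out, or that the safety result is biased. No text directs omission, and several provisions point towards reporting. In a double-blind trial, one site's habit applies to both arms.

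What the defence does not remove is that the parenthesis, as written, is not confined to the list. Had it been meant only to apply the list, it would add little, because most entries turn on facts.

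**Conclusion.** The concern holds as a problem of an unbounded rule. Section 11.1 lets an unplanned admission outside the exemption list be classed as non-serious without stated grounds, in tension with that list and with the doubt rule in 11.2. The consequence is limited to the seriousness label: the event leaves the SAE comparison and the expedited report. An on-treatment admission does not vanish from the trial data or from the wider AE outcome.

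The 10-point shift assumes that the reclassified event is that patient's only SAE. The effect is mainly descriptive and has no expected direction under blinding. It still deserves correction, because descriptive safety is a main product of a pilot of this size. Variation between sites is conditional on PI meaning the site investigator.

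**What to change.** In section 11.1, delete the parenthesis, or limit it to applying the list of exempt hospitalizations that follows. State that the list is exhaustive, so that every other inpatient admission or prolongation is an SAE, including one that also meets ILD worsening criterion 4.5.2(c).

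Keep investigator judgement for causality, for important medical events, and for the list entries that call for it. Confining the PI to causality alone would clash with the medical judgement that section 11.1 itself requires for important medical events.

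The change is about two sentences and alters no treatment rule. The downside is a few more SAE reports.

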11.2 Reporting of Serious Adverse Events Associated with Abatacept

Immediate Reporting Requirements:

Non-serious AEs and SAEs whether or not related to the BMS product associated to this study, pregnancies, AEs associated with maternal exposure, and pregnancy outcomes ascertained in the study must be reported individually in the time frames noted below. All AEs collected will also be reported in aggregate in the final study report. Any component of a study endpoint that is considered related to study therapy (e.g., death is an endpoint, if death occurred due to anaphylaxis, anaphylaxis must be reported) should be reported as an SAE.

Serious Adverse Event Collection and Reporting

- All Serious Adverse Events (SAEs) that occur following the subject's written consent to participate in the study through 30 days of discontinuation of dosing must be reported to BMS Worldwide Safety. If applicable, SAEs must be collected that relate to any later protocol-specified procedure (e.g., a follow-up skin biopsy).
- The MedWatch form 3500A will be used to report SAEs. The form will be reviewed and approved by BMS. The BMS protocol ID number must be included on whatever form is submitted by the Sponsor/Investigator. The form can be accessed at: <http://www.accessdata.fda.gov/scripts/medwatch/>.
- Following the subject's written consent to participate in the study, all SAEs, whether related or not related to study drug, are collected, including those thought to be associated with protocol-specified procedures. The investigator should report any SAE occurring after these time periods that is believed to be related to study drug or protocol-specified procedure. For drugs with potential for delayed SAEs (e.g., delayed excretion of the parent or active metabolites), a longer follow-up period may be warranted to allow collection of these SAEs Laboratory tests, and other assessments.
- For studies with long-term follow-up periods in which safety data are being reported, include the timing of SAE collection.
- The Sponsor will reconcile the clinical database SAE cases (case level only) transmitted to BMS Global Pharmacovigilance ([contact]). *Frequency of reconciliation should be every 3 months and prior to the database lock or final data summary. BMS GPV&E will email, upon request from the Investigator, the GPV&E reconciliation report. Requests for reconciliation should be sent to [contact]. The data elements listed on the GPV&E reconciliation report will be used for case identification purposes. If the Investigator determines a case was not transmitted to BMS GPV&E, the case should be sent immediately to BMS.*
- In accordance with local regulations, BMS will notify investigators of all reported SAEs that are suspected (related to the investigational product) and unexpected (i.e., not previously described in the IB). An event meeting these criteria is termed a Suspected, Unexpected Serious Adverse Reaction (SUSAR). Investigator notification of these events will be in the form of SUSAR Report.
 - Other important findings which may be reported by BMS as an ESR include: increased frequency of a clinically significant expected SAE, an SAE considered

associated with study procedures that could modify the conduct of the study, lack of efficacy that poses significant hazard to study subjects, clinically significant safety finding from a nonclinical (e.g., animal) study, important safety recommendations from a study data monitoring committee, or sponsor decision to end or temporarily halt a clinical study for safety reasons.

- Upon receiving an ESR from BMS, the investigator must review and retain the ESR with the IB. Where required by local regulations or when there is a central IRB/IEC for the study, the sponsor will submit the ESR to the appropriate IRB/IEC. The investigator and IRB/IEC will determine if the informed consent requires revision. The investigator should also comply with the IRB/IEC procedures for reporting any other safety information.
- In addition, suspected serious adverse reactions (whether expected or unexpected) shall be reported by BMS to the relevant competent health authorities in all concerned countries according to local regulations (either as expedited and/or in aggregate reports).

Investigators should report to the responsible regulatory authority as appropriate.

All SAEs must be reported by confirmed facsimile (fax) transmission or reported via electronic mail to:

SAE Email Address: [contact]

SAE [contact]

SAEs, whether related or not related to study drug, as well as pregnancies, must be reported to BMS within 24 hours. SAEs must be recorded on the MedWatch form; pregnancies must be reported on a Pregnancy Surveillance Form.

- An SAE report should be completed for any event where doubt exists regarding its seriousness.
- For studies with long-term follow-up periods in which safety data are being reported, include the timing of SAE collection in the protocol.
- If the investigator believes that an SAE is not related to study drug, but is potentially related to the conditions of the study (such as withdrawal of previous therapy or a complication of a study procedure), the relationship should be specified in the narrative section of the SAE Report Form.
- If only limited information is initially available, follow-up reports are required. (Note: Follow-up SAE reports should include the same investigator term(s) initially reported.)

If an ongoing SAE changes in its intensity or relationship to study drug or if new information becomes available, a follow-up SAE report should be sent within 24 hours to BMS (or designee) using the same procedure used for transmitting the initial SAE report. All SAEs should be followed to resolution or stabilization.

Non-serious Adverse Event Collection and Reporting

The collection of non-serious AE information should begin at initiation of study drug. All non-serious adverse events (not only those deemed to be treatment-related) should be collected continuously during the treatment period and for a minimum of 30 days following the last dose of study treatment.

All non-serious AEs must be reported by confirmed fax transmission or reported via electronic mail to:

Non-serious AE Email Address: [contact]

Non-serious AE [contact]

Non-serious AEs should be followed to resolution or stabilization, or reported as SAEs if they become serious. Follow-up is also required for non-serious AEs that cause interruption or discontinuation of the BMS product associated with this study and for those present at the end of the study, as appropriate.

MedWatch 3500A Reporting Guidelines

In addition to completing appropriate patient demographic and suspect medication information, the report should include the following information within the Event Description (section 5) of the MedWatch 3500A form:

- Treatment regimen (dosing frequency, combination therapy)
- Protocol description (and number, if assigned)
- Description of event, severity, treatment, and outcome if known
- Supportive laboratory results and diagnostics
- Investigator's assessment of the relationship of the adverse event to each investigational product and suspect medication

Follow-up information:

Additional information may be added to a previously submitted report by any of the following methods:

- Adding to the original MedWatch 3500A report and submitting it as follow-up
- Adding supplemental summary information and submitting it as follow-up with the original MedWatch 3500A form
- Summarizing new information and faxing it with a cover letter including subject identifiers (i.e. D.O.B. initial, subject number), protocol description and number, if assigned, suspect drug, brief adverse event description, and notation that additional or follow-up information is being submitted (The patient identifiers are important so that the new information is added to the correct initial report)

